5.2.2. Procedures for randomization

Patient eligibility will be established before randomized treatment assignment (see Section 4 for inclusion and exclusion criteria). The randomization will be stratified for disease status at baseline (MCI due to AD or mild AD).

The stratified randomization schedule will be prepared by the CCl Biostatistics

Department on behalf of the sponsor. Randomization codes will be allocated in blocks within strata to AZD3293 20 mg, AZD3293 50 mg, or placebo in a ratio of 1:1:1, stratified by MCI due to AD and mild AD dementia. Enrollment rates in MCI due to AD and mild AD strata will be monitored.

If a patient withdraws from the study, the patient's study identifier and randomization code will not be reused, and the patient will not be allowed to re-enter the study.

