12.3.2. Biomarkers

This section summarizes the sample-size estimates and power calculations for biomarkers arising from the CSF and PET sub-studies and for volumetric MRI data. All biomarker analyses will use α =0.05 (2-sided).

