12.3.2.1. CSF biomarkers

It is expected that at least 175 patients will be included in the CSF sub-study. Three CSF biomarkers will be assessed: $A\beta_{1-42}$, total tau, and phosphorylated tau. Assuming a 40% missed post-baseline test rate, approximately 35 patients per treatment group will have a baseline value and a post-randomization value. Estimated treatment differences are based on data from the Alzheimer's Disease Neuroimaging Initiative Pool C (www.adni-info.org).

The expected mean (SD) change in CSF $A\beta_{1-42}$ over 104 weeks is -164 (63.25) units. The minimum detectable AZD3293 difference from placebo is 49.72 units (30% reduction) with 90% power and 43 units (26% reduction) with 80% power, α =0.05 (2-sided, t-test).

The expected mean (SD) change in CSF total tau over 104 weeks is -103 (61) units. The minimum detectable AZD3293 difference from placebo is 41.4 units (47% reduction) with 90% power and 43 units (40% reduction) with 80% power, α=0.05 (2-sided, t-test).

The expected mean (SD) change in CSF phosphorylated tau over 104 weeks is -36 (18) units. The minimum detectable AZD3293 difference from placebo is 14 units (39% reduction) with 90% power and 12 units (33% reduction) with 80% power, α =0.05 (2-sided, t-test).

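### The CSF total-tau power statement pairs a smaller detectable difference with 90% power than with 80%; on the protocol's own inputs 41.4 units has 80% power, and 90% needs about 48 units

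*Protocol*

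**What the plan says.** Section 12.3.2.1 of the protocol sets out what the CSF sub-study can detect. On size it says: "It is expected that at least 175 patients will be included in the CSF sub-study". It continues: "Assuming a 40% missed post-baseline test rate, approximately 35 patients per treatment group will have a baseline value and a post-randomization value". Randomization is 1:1:1 (Section 5.2.2).

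For total tau the planning values are: "The expected mean (SD) change in CSF total tau over 104 weeks is -103 (61) units". The minimum detectable difference from placebo is then given as "41.4 units (47% reduction) with 90% power and 43 units (40% reduction) with 80% power", for a two-sided t-test at 0.05. Section 12.3.2 sets the same two-sided 0.05 level for all biomarker analyses.

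The two neighbouring lines have the same form. A-beta 1-42, mean change -164 (SD 63.25), is given 49.72 units (30%) at 90% power and 43 units (26%) at 80%. Phosphorylated tau, mean change -36 (SD 18), is given 14 units (39%) at 90% and 12 units (33%) at 80%.

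**The concern.** The total-tau sentence fails on sight in two ways. First, moving from 80% to 90% power lowers the detectable difference from 43 to 41.4 units, although asking for more power can only raise it. In the other two CSF lines it does rise. Second, the percentages run in the correct direction (47% at 90%, 40% at 80%) while the units run the other way, so the sentence contradicts itself.

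Total tau is a secondary biomarker endpoint (Section 2.2, Table 1) and belongs to the biomarker family tested at 0.05 (Section 12.2.3). A reader who takes 41.4 units at 90% power at face value would credit the sub-study with more sensitivity than its inputs support. That matters most when interpreting a null tau result.

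**Working it through.** **Inputs.** Evaluable patients per group: 175 × 0.6 / 3 = 35 (Section 12.3.2.1, with 1:1:1 allocation from Section 5.2.2). SD 61 and mean change 103 in absolute value (Section 12.3.2.1). Two-sided alpha 0.05, two-sample t-test (Sections 12.3.2 and 12.3.2.1).

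**Formula.** Standard error of the difference: SE = SD × √(2/n). Noncentrality: δ = difference / SE. Power = P(T > t₀.₉₇₅,₆₈), where T is noncentral t with 68 degrees of freedom and noncentrality δ. The detectable difference is the value that gives the required power.

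**Method check on the neighbouring lines (n = 35 per group).**

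| Marker | SD | Power | Stated difference | Recomputed difference | Power at stated difference |
|---|---|---|---|---|---|
| A-beta 1-42 | 63.25 | 90% | 49.72 | 49.72 | 90.0% |
| A-beta 1-42 | 63.25 | 80% | 43 | 42.97 | 80.1% |
| Phosphorylated tau | 18 | 90% | 14 | 14.15 | 89.4% |
| Phosphorylated tau | 18 | 80% | 12 | 12.23 | 78.5% |

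The A-beta line is reproduced to the printed precision. The phosphorylated-tau line agrees once the recomputed values are rounded to whole units. This is therefore the method the protocol used.

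**Total tau.** SE = 61 × √(2/35) = 14.58.

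| Power | Stated difference | Recomputed difference | Power at stated difference |
|---|---|---|---|
| 90% | 41.4 | 47.95 | 79.9% |
| 80% | 43 | 41.44 | 82.8% |

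- At 41.4 units, δ = 41.4 / 14.58 = 2.84.
- At 43 units, δ = 43 / 14.58 = 2.95.
- The normal approximation gives detectable differences of 47.27 and 40.85, and powers of 81.0% at 41.4 units and 83.9% at 43 units.

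**Units against percentages.**

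- 41.4 / 103 = 40.2%, printed as 47%.
- 43 / 103 = 41.7%, printed as 40%.
- 47.95 / 103 = 46.6%, which rounds to 47%.
- 41.44 / 103 = 40.2%, which rounds to 40%.

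The printed percentages match the recomputed differences; the printed units do not match the percentages.

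**Could another reading rescue it?**

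| Variant | Power at 41.4 | Power at 43 |
|---|---|---|
| One-sided 0.05 | 87.8% | 89.9% |
| Two-sided 0.025 | 70.7% | 74.3% |
| Placebo 35 against pooled doses 70 | 90.1% | 92.1% |
| 58 per group (no missing data) | 95.2% | 96.4% |

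None gives 90% at 41.4 together with 80% at 43, and none can, because power increases with the difference in every row. The pooled comparison reaches 90% at 41.4 units, but Section 12.3.2.1 does not describe pooling and the other figure would then be 92%.

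**Size of the gap.** At SD 61, 90% power at 41.4 units needs about 47 evaluable per group (46 give 89.6%, 47 give 90.2%). With 40% missing that is 47 × 3 / 0.6 = 235 patients, against the 175 stated as a minimum.

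**The case against.** The arithmetic cannot be defended, but the consequence is limited, for four reasons.

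- **The percentages are correct.** A reader who uses 47% and 40% gets the right answer. The 80% unit value errs on the cautious side, since 43 units has 82.8% power. Only the 90% unit value is optimistic.
- **Nothing is derived from this line.** The sub-study is set at 175 or more (Sections 3.1.1 and 12.3.2.1) and the detectable differences are reported afterwards. The trial's overall size rests on ADAS-Cog13 (Section 12.3.1), and the biomarker family is separate from the primary and key secondary hypotheses.
- **The planned analysis is not a plain t-test.** Section 12.2.5 specifies a repeated-measures model adjusted for predose value, disease status and APOE4, and 175 is a floor. The true power at 41.4 units is therefore not known from the protocol.
- **The cause of the slip is not documented.**

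All four points stand. They limit the weight of the finding but do not rescue the sentence, which names the t-test and gives a pair of figures that no choice of inputs can satisfy together.

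**Conclusion.** The total-tau statement is wrong as written. On the protocol's own inputs, 41.4 units has 79.9% power, so the type II error there is about 20%, twice the 10% claimed. The difference detectable with 90% power is 47.95 units, 16% above the printed value (47.95 / 41.4 = 1.16).

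This assumes exactly 35 evaluable per group, SD 61 and an unadjusted two-sided 0.05 t-test. The impossible ordering does not depend on those values. The statement that only total tau is wrong covers the three CSF lines.

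The likely cause is transcription: 41.4 is the 80% value, and 43 is the 80% value of the A-beta line. In support of this, 80% power at 43 units with 35 per group implies an SD of 63.3, close to the A-beta SD of 63.25 and not to 61. This is inference, and the conclusion does not rest on it. The error should be corrected, but it has no effect on the design.

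**What to change.** Restate the total-tau sentence in Section 12.3.2.1 as: minimum detectable AZD3293 difference from placebo 48 units (47% reduction) with 90% power and 41.4 units (40% reduction) with 80% power, two-sided 0.05 t-test. The sponsor should confirm the figures against its own calculation before reissuing the text.

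The cost is one sentence. The percentages, the sub-study size, the significance level and the analysis stay as they are. The only visible effect is a less favourable 90% figure in units.

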12.3.2.2. PET biomarkers

To explore the effect of AZD3293 on brain amyloid plaque using PET, 900 patients will be enrolled in the florbetapir F 18 amyloid PET sub-study to yield 540 patients with a baseline and post-randomization value (assuming a 40% missed post-baseline test rate). Based on the ADNI

^{*}The overall population effect sizes and power calculations use a distribution of 65% mild AD patients and 35% MCI patients.

study results, using florbetapir as the radioligand, the expected mean \pm SD change in amyloid load over 104 weeks is 0.0484 ± 0.0979 in SUVR-equivalent units (for patients with a baseline amyloid load of 1.15 to 1.38) in the placebo treatment group. Accordingly, the minimum detectable AZD3293 difference from placebo is 0.036 units (a 75% reduction) in the slope of A β accumulation with 92.1% power, and .041 units (a 85% reduction) with 97.5% power; α =0.05 (2-sided, t-test). Estimated treatment differences are based on data from the Alzheimer's Disease Neuroimaging Initiative (www.adni-info.org): University of Berkeley analysis of florbetapir longitudinal data, only including subjects who have moderately positive amyloid load in brain (SUVR in cortex was 1.15 to 1.38 at baseline).

12.3.2.3. MRI biomarkers

Volumetric MRI data will be obtained from all 2202 patients enrolled in the study. Assuming a 30% dropout rate, it is expected that 1541 patients (approximately 514 per treatment group) will complete the study. Assuming a mean (SD) decrease of 7.565 (5.242) units in MRI brain volume by Week 104 in the placebo group, the minimum detectable AZD3293 difference from placebo is 1.367 units (an 18% reduction) with greater than 99% power and α=0.05 (2-sided, t-test). Estimated treatment differences are based on data from the Alzheimer's Disease Neuroimaging Initiative Pool C (www.adni-info.org).

12.3.3. Pharmacogenetics

The number of patients who will agree to participate in the optional genetic research is unknown. It is therefore not possible to establish whether sufficient data will be collected to allow a formal statistical evaluation or whether only descriptive statistics will be generated. A separate Statistical Analysis Plan will be prepared where appropriate.

12.4. Data monitoring committee

This study will use an IDMC to monitor data on an ongoing basis to ensure the continuing safety of patients enrolled in the study, to ensure the integrity of the blinded nature of the study, and to oversee the interim analyses (see Section 12.2.2). The IDMC will be composed of individuals external to the sponsor and will consist of a Chair, plus at least 1 medical expert in the relevant therapeutic area and at least 1 statistician. The IDMC recommendations may include, but will not be limited to, the following:

- Continue the study as designed
- Modify the study and continue (including discontinuation of an AZD3293 dose group)
- Stop the study (for reasons of safety, conduct, or external information)

An IDMC charter will be developed which will specify the Committee's responsibilities, authorities, and procedures along with details of the interim analysis planning, decision-making guidance, and dissemination of the results as well as the recommendations and decisions after the interim analyses (see Section 12.2.2.). Formal implementation and communication of IDMC

recommendations will be managed by the sponsor Executive Committee, chaired by the sponsor Chief Medical Officer and unrelated to the AZD3293 project team, will receive and act on the recommendations from the IDMC. A firewall will be established to ensure the maintenance of the study blind for the sponsor, the investigational site staff, and study patients and their study partners.

13. IMPORTANT MEDICAL PROCEDURES TO BE FOLLOWED BY THE INVESTIGATOR

13.1. Medical emergencies and sponsor contacts

The Principal Investigator is responsible for ensuring that procedures and expertise are available to handle medical emergencies during the study. A medical emergency usually constitutes an SAE and is to be reported as such, see Section 6.4.4

In the case of a medical emergency the Investigator may contact the CCI Study Physician.

The treatment code may not be broken except in an emergency situation when the appropriate management of the patient necessitates knowledge of the treatment allocation. In such an emergency, the investigator will, if time and circumstances permit, contact the local sponsor representative prior to breaking the treatment code (see Section 5.4.2).

13.2. Overdose

If a patient takes more than 2 total daily doses of study medication in a 24-hour period, it will be considered an overdose.

There are currently no data regarding overdosing of AZD3293, and there is no known antidote for AZD3293. In case of overdose, monitoring of cardiac, hepatic and hematological effects is essential, and appropriate standard support therapy should be initiated where clinically indicated.

If an overdose on study medication occurs in the course of the study, then investigators or other site personnel must inform appropriate sponsor representatives including the sponsor-designated medical monitor. A blood sample for determination of plasma AZD3293 concentration should be obtained if at all possible, and as soon as possible after the overdose becomes known, if associated with an AE.

An overdose without associated symptoms is only recorded on the Overdose CRF.

An overdose with associated AEs is recorded as the AE diagnosis/symptoms on the relevant AE modules in the CRF and on the Overdose CRF.

For overdoses associated with SAEs, standard reporting timelines and procedures apply, see Section 6.4.4. The Overdose CRF is also completed.

13.3. Pregnancy

All outcomes of pregnancy either in a study patient or pregnant partner should be reported to the sponsor.

13.3.1. Maternal exposure

Women of childbearing potential are not allowed to be included in this study. Should a pregnancy still occur during study treatment, the patient should be discontinued from the study immediately (as described in Section 5.3) and the pregnancy reported to the sponsor. Any pregnancy occurring from the date of the first dose of study treatment until 90 days after the last

dose and any pregnancy occurring within 90 days after amyloid PET scan should be reported to the sponsor and followed up for its outcome as described below.

Pregnancy itself is not regarded as an AE unless there is a suspicion that the investigational product under study may have interfered with the effectiveness of a contraceptive medication. Congenital abnormalities/birth defects and spontaneous miscarriages should be reported and handled as SAEs. Elective abortions without complications should not be handled as AEs. The outcome of all pregnancies (spontaneous miscarriage, elective termination, ectopic pregnancy, normal birth or congenital abnormality) should be followed up and documented even if the patient was discontinued from the study.

If any pregnancy occurs in the course of the study, then investigators or other site personnel inform appropriate sponsor representatives immediately, or **no later than 24 hours** of when he or she becomes aware of it. Pregnancies are to be reported to the sponsor representatives using the Pregnancy Notification provided.

The same timelines apply when outcome information is available.

13.3.2. Paternal exposure

Pregnancy of a patient's sexual partner is not considered to be an AE. However, any conception occurring from the date of the first dose until 90 days after the last dose and any pregnancy occurring within 90 days after amyloid PET scan should be reported to the sponsor and followed up for its outcome (spontaneous miscarriage, elective termination, ectopic pregnancy, normal birth or congenital abnormality).

Appendix B. Additional Safety Information

Clinical Study Protocol Appendix B

Drug Substance AZD3293 [LY3314814]

Study Code D5010C00009 [I8D-MC-AZES]

Edition Number 7.1

Date See Cover Page

FURTHER GUIDANCE ON THE DEFINITION OF A SERIOUS ADVERSE EVENT (SAE)

Life threatening

"Life-threatening" means that the subject was at immediate risk of death from the AE as it occurred or it is suspected that use or continued use of the product would result in the subject's death. "Life-threatening" does not mean that had an AE occurred in a more severe form it might have caused death (eg, hepatitis that resolved without hepatic failure).

Hospitalization

Outpatient treatment in an emergency room is not in itself a serious AE, although the reasons for it may be (eg, bronchospasm, laryngeal edema). Hospital admissions and/or surgical operations planned before or during a study are not considered AEs if the illness or disease existed before the subject was enrolled in the study, provided that it did not deteriorate in an unexpected way during the study.

Important medical event or medical intervention

Medical and scientific judgement should be exercised in deciding whether a case is serious in situations where important medical events may not be immediately life threatening or result in death, hospitalisation, disability or incapacity but may jeopardize the subject or may require medical intervention to prevent one or more outcomes listed in the definition of serious. These should usually be considered as serious.

Simply stopping the suspect drug does not mean that it is an important medical event; medical judgement must be used.

Examples of such events are:

- Angioedema not severe enough to require intubation but requiring iv hydrocortisone treatment
- Hepatotoxicity caused by paracetamol (acetaminophen) overdose requiring treatment with N-acetylcysteine

- Intensive treatment in an emergency room or at home for allergic bronchospasm
- Blood dyscrasias (eg, neutropenia or anemia requiring blood transfusion, etc) or convulsions that do not result in hospitalization
- Development of drug dependency or drug abuse.

A GUIDE TO INTERPRETING THE CAUSALITY QUESTION

The following factors should be considered when deciding if there is a "reasonable possibility" that an AE may have been caused by the drug.

- Time course. Exposure to suspect drug. Has the subject actually received the suspect drug? Did the AE occur in a reasonable temporal relationship to the administration of the suspect drug?
- Consistency with known drug profile. Was the AE consistent with the previous knowledge of the suspect drug (pharmacology and toxicology) or drugs of the same pharmacological class? OR could the AE be anticipated from its pharmacological properties?
- Dechallenge experience. Did the AE resolve or improve on stopping or reducing the dose of the suspect drug?
- No alternative cause. The AE cannot be reasonably explained by another etiology such as the underlying disease, other drugs, other host or environmental factors.
- Rechallenge experience. Did the AE reoccur if the suspected drug was reintroduced after having been stopped? The sponsor would not normally recommend or support a rechallenge.
- Laboratory tests. A specific laboratory investigation (if performed) has confirmed the relationship?

A "reasonable possibility" could be considered to exist for an AE where one or more of these factors exist.

In contrast, there would not be a "reasonable possibility" of causality if none of the above criteria apply or where there is evidence of exposure and a reasonable time course but any dechallenge (if performed) is negative or ambiguous or there is another more likely cause of the AE.

In difficult cases, other factors could be considered such as:

- Is this a recognised feature of overdose of the drug?
- Is there a known mechanism?

Ambiguous cases should be considered as being a "reasonable possibility" of a causal relationship unless further evidence becomes available to refute this. Causal relationship in cases

where the disease under study has deteriorated due to lack of effect should be classified as no reasonable possibility.

Appendix C. International Airline Transportation Association (IATA) 6.2 Guidance Document

Clinical Study Protocol Appendix C

Drug Substance AZD3293 [LY3314814]

Study Code D5010C00009 [I8D-MC-AZES]

Edition Number 7.1

Date See Cover Page

Content from Appendix C is being removed from the protocol to allow for potential changes in guidelines and local laws. The confirmation that study sample shipping materials are aligned with International Airline Transportation Association (IATA) certification is contained in the Study Laboratory Manual. The confirmation that the site has at least one IATA certified individual is covered during the site selection process and monitoring.

Appendix D. Actions Required in Cases of Combined Increase of Aminotransferase and Total Bilirubin - Hy's Law

Clinical Study Protocol Appendix D

Drug Substance AZD3293 [LY3314814]

Study Code D5010C00009 [I8D-MC-AZES]

Edition Number 7.1

Date See Cover Page

1. Introduction

During the course of the study the Investigator will remain vigilant for increases in liver biochemistry. The investigator is responsible for determining whether a subject meets potential Hy's Law (PHL) criteria at any point during the study.

The Investigator participates, together with the sponsor's clinical project representatives, in review and assessment of cases meeting PHL criteria to agree whether Hy's Law (HL) criteria are met. HL criteria are met if there is no alternative explanation for the elevations in liver biochemistry other than Drug Induced Liver Injury (DILI) caused by the Investigational Medicinal Product (IMP).

The Investigator is responsible for recording data pertaining to PHL/HL cases and for reporting Adverse Events (AE) and Serious Adverse Events (SAE) according to the outcome of the review and assessment in line with standard safety reporting processes.

2. Definitions

Potential Hy's Law (PHL)

Aspartate Aminotransferase (AST) or Alanine Aminotransferase (ALT) \geq 3x Upper Limit of Normal (ULN) **and** Total Bilirubin (TBL) \geq 2xULN at any point during the study irrespective of an increase in Alkaline Phosphatase (ALP). The elevations do not have to occur at the same time or within a specified time frame.

Hy's Law (HL)

AST or ALT \geq 3x ULN and TBL \geq 2xULN, where no other reason, other than the IMP, can be found to explain the combination of increases, eg, elevated ALP indicating cholestasis, viral hepatitis, another drug. The elevations do not have to occur at the same time or within a specified time frame.

3. Identification of potential Hy's law cases

In order to identify cases of PHL it is important to perform a comprehensive review of laboratory data for any subject who meets any of the following identification criteria in isolation or in combination:

- ALT $\geq 3xULN$
- AST $\geq 3xULN$
- TBL $\geq 2xULN$

The Investigator will without delay review each new laboratory report and if the identification criteria are met will:

- Notify the sponsor representative
- Determine whether the subject meets PHL criteria (see Section 2 of this Appendix for definition) by reviewing laboratory reports from all previous visits

4. Follow-up

